10.6.5 Safety analyses

Safety analyses will be conducted on the safety analysis set. The main safety analyses will compare descriptively between AE rates for Steal, Infection, Aneurysm and Seroma as described in section 10.2.2. That is, we will present point estimates along with Exact Binomial, two-sided, 95% confidence intervals for each of these events separately for both our study and Schinstock et al.

Additionally, descriptive statistics will be provided, with SAE's and AE's coded by body system, preferred term, arm, severity, relation to procedure by arm and outcome. Rate of freedom from major device-related adverse events will be provided along with associated two-sided 95% Exact Binomial confidence intervals.

In addition to the dichotomously scored endpoints we will also present frequency and percent for grade for steal (mild; moderate; severe), infection (resolved with antibiotic; loss of AV; loss of limb) and seroma (resolved without treatment; aspirated, surgical treatment; loss of AV access).

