3 STUDY OBJECTIVES

The study is designed to clinically demonstrate safety and effectiveness of the VasQ in the following aspects:

1. Demonstrate the potential of the VasQ in meeting the specified performance goal in primary patency of AV fistulas.
2. Demonstrate the safety of the VasQ in vascular access.

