10.2.1 Historical safety data

A search of the literature yielded two papers with data on non-thrombotic complications up to a period of 6 months. Based on these papers, SOC fistula safety can be estimated, whose rates with respect to the steal, infection, aneurysm, and seroma are presented in Table 10-1 below:

Table 10-1: Safety data from literature

Paper	Country	N	Steal (%)	Infection (%)	Aneurysm (%)	Seroma (%)	Overall rate [#]
Schinstock et al. Outcomes of Arteriovenous Fistula Creation after the Fistula First Initiative. Clin J Am Soc Nephrol 6: 1996–2002, 2011	USA	293	5.1	7.5	2.4	1.4	7.5 - 16.4
Dunlop et al. Vascular access: experience with the brachiocephalic fistula. Annals of the Royal College of Surgeons of England (1986) vol. 68	Scotland	77	6.5	2.6	3.9	NR*	6.5 – 13.0

Document title: VasQ FDA pivotal Protocol	Document No. CD0121	Revision 12.0 14 March 2021	Page 31 of 42
--	------------------------	-----------------------------------	------------------

*NR=Not reported

*Assuming no subject experienced more than one AE (which we know is not the case) the rate for experiencing any AE is the sum of the rates. Assuming every subject experienced all of the AEs (which we know is not the case) the rate experiencing any AE is the largest percentage reported

Note that:

- The study done in 1986 reports relatively similar rates to the most recent study. The SOC in this indication has changed little in 40 years so that we can expect older data to be as valid for comparison as newer.
- The Schinstock et al study was done in the Mayo Clinic in the US and included nearly 300 patients. For this reason, we propose it as the main comparison to the data to be collected in our own study.
- Importantly, AE rates are reported separately for the each of the four AEs allowing for a detailed comparison of new treatment to the SOC
- The rates reported in the above table overlap so that the average number of AEs for subjects who had these AEs is more than one. Neither of the papers provides an overall rate of subjects who experienced any of the four AEs.

Several additional papers which report data on one or more of the four complications are provided in Table 10-2 in support of the safety values to which the study observed data can be compared. Overall, it can be observed that values for all 4 events converge around single digit incidence rate for each event.

Table 10-2: Additional safety data from the literature

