10.2.2 Methodology for assessing safety

Laminate believes that the most appropriate way for assessing safety in the current study is to compare the rates for each type of AE obtained in the study with those reported in the literature. Such a multidimensional comparison will provide a more complete picture of the VasQ's safety profile than comparing an overall rate combining AEs with different clinical implications. Given the four comparisons, we feel it is most appropriate they be done descriptively. First, because statistical testing would involve 4 separate tests, along with associated issues of Type I Error and power (for success in all 4). Second, as noted, neither study provides overall, non-overlapping rates for these four non-thrombotic AEs, nor can this be obtained from the more detailed data presented in the articles (and shown in the preceding section). For this reason a statistical comparison of overall AEs rate cannot be done.

It is important to add that a descriptive comparison of each of the 4 rates between the current trial and Schinstock et al. is meaningful given that the precision of each of the (relatively small) rates is 2% to 4%; i.e. given the small AE rates involved, the planned N for our study of 116 evaluable patients will provide good precision that, in turn, will provide a meaningful comparison between our rates and those reported by Schinstock et al. In addition, even the upper bound higher rate (16.4%) has a precision of 4%. Precision is here defined as the half width of the two sided, 95% confidence interval computed using the Exact Binomial method.

Consequently, we propose evaluating safety in our trial by presenting the 4 AEs listed along with associated two-sided, 95%, Exact Binomial confidence interval to those presented in Schinstock et al. In conclusion, we feel that the most appropriate safety assessment for the VasQ is by:

- Evaluating each of the four AEs of interest separately
- Presenting safety data with two-sided 95% confidence intervals of high precision; i.e. that are relatively narrow at $\pm 3\%$ to 4%

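### Objective 2 is to demonstrate safety, but the main safety analysis shows two separate sets of 95% intervals and gives no interval for the difference that readers are meant to judge

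*Combined protocol and SAP*

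**What the plan says.** Section 3 and the Synopsis give the second objective as "Demonstrate the safety of the VasQ in vascular access". The main safety analysis in section 10.6.5 is descriptive: "we will present point estimates along with Exact Binomial, two-sided, 95% confidence intervals for each of these events separately for both our study" and for the 293-patient US comparator study.

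Section 10.2.2 explains this choice: "Given the four comparisons, we feel it is most appropriate they be done descriptively". It gives two reasons. The first is that "statistical testing would involve 4 separate tests, along with associated issues of Type I Error and power (for success in all 4"). The second is that no overall, non-overlapping rate is available from the literature.

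The section says that the planned sample "will provide a meaningful comparison between our rates and those reported by" the comparator, because "the precision of each of the (relatively small) rates is 2% to 4" per cent at 116 evaluable patients. Neither section sets a margin, a limit to beat, an interval for the difference, or a rule for reading the display.

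**The concern.** The question that the display invites is whether VasQ has more of these events than the comparator, and by how much. That is a question about four differences, and the plan estimates none of them. Two separate 95% intervals can overlap when the 95% interval for the difference excludes zero, so overlap can be mistaken for similarity.

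The plan's reasons for not testing do not reach this point. Multiplicity and power argue against four hypothesis tests. They do not argue against four estimates with intervals, which stay descriptive. Limited power is also a reason not to promise a demonstration. Effectiveness, by contrast, has hypotheses, a 55% goal and an explicit confidence-limit rule (section 10.6.3). For safety, the conclusion would depend on how the display is read once the data are in.

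**Working it through.** **Inputs.** The comparator row of Table 10-1 reads "293 5.1 7.5 2.4 1.4 7.5 - 16.4": N, then steal, infection, aneurysm, seroma, and the range for the overall rate. Counts are back-calculated from the rounded percentages: 0.051, 0.075, 0.024 and 0.014 × 293 = 14.9, 22.0, 7.0 and 4.1, so 15, 22, 7 and 4. VasQ N is 129 (main cohort, all implanted); 116 and 144 are variants. Doubling is this review's yardstick, since the plan names no margin.

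**The plan's own figure.** Section 10.2.2 defines precision as the half-width of the exact 95% interval. At N=116 and the comparator's rates this gives 4.5 (steal), 5.2 (infection), 3.3 (aneurysm) and 2.7 (seroma) points, and 7.1 at a 16.4% rate. The plan states 2 to 4 points, and 4 at 16.4%. Those figures are nearer to N=293 (2.7, 3.2, 2.0, 1.6 and 4.4). The intervals will be wider than the plan assumed when it called the comparison meaningful.

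**Methods.** Exact limits for x of n: lower = Beta(0.025; x, n−x+1), upper = Beta(0.975; x+1, n−x). Newcombe interval for d = p1 − p2, with Wilson limits (l, u) for each rate: d − √[(p1−l1)² + (u2−p2)²] to d + √[(u1−p1)² + (p2−l2)²].

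**Overlap can hide a difference.** Take 19/129 infections against 22/293.
- Exact intervals are 9.1% to 22.0% and 4.8% to 11.1%. They overlap.
- d = 14.73 − 7.51 = 7.22 points. Wilson limits are 9.64 to 21.86 and 5.01 to 11.11.
- Lower: 7.22 − √(5.09² + 3.60²) = 7.22 − 6.23 = +1.0.
- Upper: 7.22 + √(7.13² + 2.50²) = 7.22 + 7.56 = +14.8.

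**Chance that a true doubling goes unnoticed, per event, N=129.** For each reading, find the smallest VasQ count that would signal an excess, holding the comparator counts fixed. The miss probability is the binomial probability of a lower count at twice the tabulated rate.

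| Reading | Steal (10.2%) | Infection (15.0%) | Aneurysm (4.8%) | Seroma (2.8%) |
|---|---|---|---|---|
| Exact intervals do not overlap (counts 18, 23, 12, 10) | 89% | 78% | 98% | >99% |
| VasQ lower limit above comparator point estimate | 44% | 25% | 72% | 85% |
| VasQ point estimate above comparator upper limit | 22% | 11% | 58% | 71% |
| Newcombe interval above 0 (counts 14, 18, 9, 6) | 55.5% | 33.3% | 83.2% | 84.5% |

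The overlap row is 92%, 79%, 99% and 99.5% at N=116, and 90%, 76%, 98% and 99.7% at N=144. If sampling error in the comparator counts is included, at N=129 it is 85%, 72%, 96% and 98%.

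**What a matching result would exclude.** The comparator's rates applied to 129 give 6.6, 9.7, 3.1 and 1.8 events.

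| Event | VasQ count | Upper limit of difference | Doubling would be |
|---|---|---|---|
| Steal | 7 (or 6) | +6.0 (or +5.0) | +5.1 |
| Infection | 10 | +6.7 | +7.5 |
| Aneurysm | 3 | +4.4 | +2.4 |
| Seroma | 2 | +4.2 | +1.4 |

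Aneurysm and seroma could have doubled without being excluded. Steal depends on one event. A doubling of infection would be excluded.

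**The case against.** The strongest case for the plan has five parts.

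- **No overlap rule is stated.** A reader might infer that the planned comparison would miss a doubling 78% to more than 99% of the time. The documents do not support that as a property of the plan, because it needs a non-overlap rule that appears nowhere in them. Other readings of the same display at N=129 give 11% to 85%. This objection stands.
- **A difference interval is not a cure.** It still misses a doubling 33% to 85% of the time, and without a margin it leaves no decision rule. This stands too: the gain is a direct estimate, not a demonstration of safety.
- **It is not the only comparison.** Section 10.2.1 adds a second 6-month study and eight further sources. Section 6.2.1 adds cumulative event counts for comparison with the literature. Section 10.6.5 adds event grades and freedom from major device-related events, and section 12 provides independent adjudication. This is right, but none of it supplies the missing difference.
- **The cohorts differ.** Table 10-4 describes the comparator as a retrospective review of new fistulas placed in 2006-2008; the main cohort is prospective and brachiocephalic. An interval for the difference reflects sampling error only and could suggest more comparability than exists. That calls for a caveat. It applies equally to the side-by-side display, which invites the same comparison.
- **The choice was deliberate.** Descriptive reporting is defensible, and the difference intervals keep to it.

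**Conclusion.** The point holds as a mismatch between objective and analysis. The plan promises to demonstrate safety, sets no standard for doing so, and omits the interval for the difference that its comparison is about. The infection example shows that overlapping intervals can accompany a difference CI of +1.0 to +14.8 points. If VasQ matched the comparator, upper limits of about +4.4 points (aneurysm) and +4.2 points (seroma) would still allow more than a doubling.

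Two stronger inferences should be avoided. The miss rates of 78% to more than 99% hold only per event, at N=129, and for a reader who judges by overlap. Nor can it be said that no doubling could be excluded: infection would be, and steal turns on a single event.

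The figures assume comparator counts recovered from rounded percentages and held fixed, doubling as the yardstick, and 129 patients in the safety comparison. The safety set could be 144 if the forearm cohort is included.

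**What to change.** - In sections 10.2.2 and 10.6.5, add for each of the four events the rate difference (VasQ minus the 293-patient comparator) with a two-sided 95% CI, for example Newcombe. Report it descriptively, with the caveat that it is an unadjusted comparison with a historical cohort.
- State in the same sections that overlap of the two separate intervals will not be read as evidence of similar safety.
- In section 3 and the Synopsis, reword objective 2 to match a descriptive analysis, for example: characterise the rates of steal, infection, aneurysm and seroma relative to published rates.

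The cost is four intervals from counts already planned, plus the wording changes; no new patients or data are needed. The downside is visibly wide upper limits and an objective that sounds less favourable.

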10.6.6 Secondary endpoints

Secondary endpoints will be considered exploratory and will be presented descriptively, along with associated 95% confidence intervals. The analysis sets for each endpoint are as follows:

1. Time to primary patency cessation since the fistula creation - *FAS primary and FAS secondary analysis sets*
2. Time to assisted primary patency cessation since the creation - *FAS primary and FAS secondary analysis sets*
3. Time to primary patency cessation since the first intervention (post-intervention primary patency) - *FAS primary and FAS secondary analysis sets*
4. Time to assisted primary patency cessation since the first intervention (post -intervention assisted primary patency) - *FAS primary and FAS secondary analysis sets*
5. Time to first successful cannulation – *Ongoing dialysis subset*
6. Time to secondary patency cessation since the fistula creation - *FAS primary and FAS secondary analysis sets*
7. Time to secondary patency cessation since the first intervention (post intervention secondary patency) - *FAS primary and FAS secondary analysis sets*
8. Time to fistula maturation (physiological) - *FAS primary and FAS secondary analysis sets*
9. Time to 100% functional fistula dependency – *Ongoing dialysis subset*
10. Unassisted maturation at 3 months defined as vein diameter \geq 5mm and blood outflow \geq 500 (-50) mL/min by Doppler ultrasound - *FAS primary and FAS secondary analysis sets.*

Document title: VasQ FDA pivotal Protocol	Document No. CD0121	Revision 12.0 14 March 2021	Page 39 of 42
--	------------------------	-----------------------------------	------------------

11. Primary patency at 6 months post AVF creation, excluding patients who have received balloon angioplasty procedures directed at cephalic arch and central vein stenosis *FAS primary and FAS secondary analysis sets*.
12. Time to first intervention - *FAS primary and FAS secondary analysis sets*
13. Number of interventions (including type and outcome) - *FAS primary and FAS secondary analysis sets*
14. Rate of interventions per patient-years - *FAS primary and FAS secondary analysis sets*
15. Primary Failure, at 6 months, which is fistula permanent failure before hemodialysis suitability - *FAS primary and FAS secondary analysis sets*
16. Target artery / target vein flow (mL/min) at 1, 3 and 6 months by Doppler blood outflow measurement - *FAS primary and FAS secondary analysis sets*
17. Target artery /target vein diameter at 1, 3 and 6 months by Doppler measurement - *FAS primary and FAS secondary analysis sets*.
18. Target artery / target vein PSV (Peak Systolic Velocity, cm/sec) - *FAS primary and FAS secondary analysis sets*
19. Proportion of fistulas used for hemodialysis at 3 and 6 months post AVF creation - *Any dialysis subset*.
20. Duration between fistula first use for dialysis and final abandonment – *any dialysis subset*

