10.5.2 Full analysis set: Primary Effectiveness Analysis

The full analysis set for the primary effectiveness analysis (FAS_primary) will, consistent with ICH Guideline E9, include all subjects (with brachiocephalic fistulas) for whom the study device was implanted and for whom there is at least one post-procedure Primary Patency measurement.

Handling of missing data: Patients occluded prior to 6 months will be scored as failures even if missing subsequent observations. Patients with missing primary patency at 6 months, but with observed primary patency at later visits (without undergoing interventions) will be considered Success.

Because MI assumes missing at random (MAR), we will conduct sensitivity analyses to assess the sensitivity of our results to alternative assumptions of missingness (see below).

Subjects who died or underwent transplant before 6 months, and were non-occluded at that time of the event, will be excluded from the FAS and reported separately. If such subjects were occluded at or before the time of the event (death or transplant), they will be considered failures and included in FAS for the purpose of the primary analysis.

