10.5.3 Full analysis set: Secondary Effectiveness Analysis

The full analysis set for the secondary analysis (FAS_secondary), will consist of the main and supplementary cohort subjects who meet the criteria described in the preceding section for FAS_primary.

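### Time-to-event and early-visit secondary endpoints are run on a FAS that drops subjects who die or are transplanted before 6 months with an open fistula: a small, real flaw in exploratory endpoints

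*Combined protocol and SAP*

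**What the plan says.** - **Who is in the set (10.5.2).** FAS_primary takes brachiocephalic subjects "for whom the study device was implanted and for whom there is at least one post-procedure Primary Patency measurement".
- **Who is removed.** "Subjects who died or underwent transplant before 6 months, and were non-occluded at that time of the event, will be excluded from the FAS".
- **Who stays.** "If such subjects were occluded at or before the time of the event (death or transplant), they will be considered failures and included in FAS".
- **The combined set (10.5.3).** FAS_secondary takes main and supplementary cohort "subjects who meet the criteria described in the preceding section for FAS_primary", so the same rule applies.
- **Where the sets are used (10.6.6).** Endpoints 1-4, 6-8 and 10-18 are assigned to both FAS sets. They include "Time to secondary patency cessation since the fistula creation" (endpoint 6), time to first intervention (12), interventions per patient-year (14), "Unassisted maturation at 3 months defined as vein diameter" and flow (endpoint 10), and flow and diameter at 1, 3 and 6 months (16, 17). Endpoints 5, 9, 19 and 20 use dialysis subsets that are not defined by FAS membership, so they are outside this point.
- **Status.** 10.6.6 calls all secondary endpoints exploratory and descriptive, with 95% confidence intervals. Follow-up runs to 24 months (4.1).

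The readable text has no censoring rule for death or transplant and no separate analysis set for the time-to-event endpoints.

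**The concern.** The rule suits a yes/no endpoint at 6 months, where a subject who dies earlier with an open fistula has no 6-month status. In a time-to-event analysis that subject does carry information: someone event-free to day 150 who then dies should contribute 150 days and be censored. Under the plan this subject contributes nothing, while one who occludes on day 100 and then dies contributes an event. Membership of the set therefore depends on something that happens after time zero and is tied to the outcome.

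There is also a break at month 6. A subject who dies with an open fistula at month 5 leaves the set; one who dies at month 7 stays, with no stated handling.

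For visit-based endpoints the effect is different. A subject scanned at months 1 and 3 who dies at month 5 with an open fistula drops out of the 1- and 3-month summaries because of a later event. At stake are the accuracy of the patency curves and the completeness of the early Doppler tables, not the trial's success criterion.

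**Working it through.** **The plan's own figure.** The secondary endpoints have no stated figure. The only one nearby is the primary sample size (10.4). With n = 116, the exact two-sided 95% lower limit first exceeds 55% at 75 successes. At a true rate of 70% the exact power is 0.911, against a stated 90%; 116/(1 - 0.10) = 128.9, so 129 enrolled. Both reproduce, and neither depends on the point below.

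**Inputs.** N = 129 (10.4). The following are assumptions, because the documents give no rates: 6-month occlusion 15%, intervention 18%, and death or transplant d = 4% to 10%, all with independent constant hazards. Occlusion is treated as permanent and as the event that ends secondary patency.

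Write the cumulative 6-month hazards as:
- a = -ln(0.85) = 0.1625 (occlusion)
- b = -ln(0.82) = 0.1985 (intervention)
- m = -ln(1 - d) = 0.0408 at 4%, 0.1054 at 10% (death or transplant)

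**Share removed** (death or transplant before 6 months and before occlusion): q = m/(a + m) × [1 - 0.85(1 - d)].
- d = 4%: 0.2008 × 0.184 = 0.0369; × 129 = 4.8 subjects
- d = 10%: 0.3933 × 0.235 = 0.0924; × 129 = 11.9 subjects

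The same formula run only to month 3 replaces the bracket by 1 - exp[-(a + m)/2]. Subtracting that leaves about 2.3 and 5.6 subjects removed after month 3.

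**Secondary patency at 6 months (endpoint 6).** Everyone left in the set either occluded or reached month 6 open, so the estimate is 0.85(1 - d)/(1 - q). The true value is 85.0%; censoring at death or transplant would recover it under independence.
- d = 4%: 0.816/0.9631 = 84.7%, about -0.3 points
- d = 10%: 0.765/0.9076 = 84.3%, about -0.7 points

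**Primary patency curve at 6 months (endpoint 1).** True value 0.85 × 0.82 = 69.7%. The estimate is 0.82 times the line above.
- d = 4%: 69.5%, about -0.2 points
- d = 10%: 69.1%, about -0.6 points

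**Why the sign is not fixed for primary patency.** Intervention also ends primary patency (6.4), but removal depends only on being non-occluded. A subject who had an intervention and then died with an open fistula is removed together with an observed event. The share is q minus the share whose death or transplant precedes both other events, m/(a + b + m) × [1 - 0.697(1 - d)].
- d = 4%: 0.0369 - 0.0336 = 0.0033; × 129 = 0.4 subjects
- d = 10%: 0.0924 - 0.0842 = 0.0082; × 129 = 1.1 subjects

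This pulls the estimate upward. The net is downward in this model, but dependence between intervention and death could change that.

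**Interventions (12-14).** The share of subjects with a first intervention before 6 months and before death or transplant is b/(b + m) × [1 - 0.82(1 - d)] = 0.176 at 4% and 0.171 at 10%. First interventions lost: 0.0033/0.176 = 1.9% and 0.0082/0.171 = 4.8%. Removal depends only on the occlusion and death times. If intervention is independent of both, its distribution among those kept equals that in the full cohort. A simulation of this model agrees: the bias in 6-month freedom from intervention is 0.0 points at both rates. Events and exposure are lost, but no bias arises.

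**Sensitivity to the occlusion rate.** If the whole 30% loss implied by the plan's 70% assumption were occlusion, with d = 3% to 10%, the same calculation removes about 3 to 11 subjects and lowers 6-month patency from 70.0% to between 69.7% and 68.8%.

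**Visit-based endpoints (8, 10, 16-18).** No bias figure was derived. What follows from the text is that values recorded before the death or transplant leave the summaries.

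**The case against.** **The rule may be meant only for the primary endpoint.** The section title names the primary effectiveness analysis, and occluded subjects are kept with the words "they will be considered failures and included in FAS for the purpose of the primary analysis". That qualifier sits on the inclusion sentence; the exclusion sentence has none. 10.6.6 then assigns the same sets by name to the secondary endpoints. The intent may have been narrower, but the plan as written applies the exclusion.

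**Redacted lines in 6.4 may hold a censoring rule.** They may, but a censoring rule cannot act on subjects already outside the set.

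**The effect is negligible.** This largely stands. At N = 129 the approximate 95% half-width is 1.96 × √(0.85 × 0.15/129) = 6.2 points at 85% patency and 7.9 points at 70%, so the shift is about a tenth of sampling error or less. Eligibility also excludes life expectancy under 30 months and transplant expected within 6 months, which favours the lower end of the assumed range.

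**Censoring at death is itself a choice.** It assumes independence, and a competing-risk estimate is also legitimate. That affects the remedy, not the need for one.

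A reader might infer four stronger things, none of which the documents support:
- **That every affected endpoint is selected on its own outcome.** The rule selects on occlusion. Time to first intervention is not biased under independence.
- **That the bias must run against the device.** Subjects with an intervention who die with an open fistula are removed too.
- **That the data are destroyed.** These subjects are "and were non-occluded at that time of the event, will be excluded from the FAS and reported separately", and 10.6.1 promises listings by subject. The values leave the summaries, not the record.
- **That the primary result or sample size is compromised.** Neither uses these endpoints.

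**Conclusion.** The point holds as a minor but real correction. As written, the plan conditions endpoints 1, 2 and 6 on a later outcome. Under the stated assumptions this costs about 0.3 to 0.7 points of 6-month secondary patency and 0.2 to 0.6 points on the primary patency curve, with the sign for primary patency not guaranteed. Endpoints 12-14 lose about 2% to 5% of first interventions, with the matching exposure. Endpoints 8, 10 and 16-18 lose valid earlier observations from their summaries.

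The structural finding rests on the text alone. The sizes rest on assumed event rates and on independence, and they grow with the rates of occlusion and of death or transplant. The endpoints are exploratory and the primary test does not change.

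**What to change.** In 10.6.6:
1. Analyse endpoints 1-4, 6-8, 10, 12-14 and 16-18 on all implanted subjects with any post-procedure data, for the main cohort and for both cohorts combined.
2. Censor time-to-event endpoints at death, or at transplant with a functioning fistula, whether before or after month 6. A competing-risk estimate can be an optional sensitivity analysis.
3. Use every visit value observed before that date for the maturation, flow, diameter and PSV endpoints.
4. Keep the death/transplant exclusion of 10.5.2 only for the 6-month binary endpoints (the primary endpoint, and secondary endpoints 11 and 15).

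This is a change of SAP wording and needs no new data. The cost is that denominators will differ between the primary and secondary tables, which a footnote should explain.
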